10.3.2 Safety and tolerability analysis

10.3.2.1 Analysis for Primary Variables

The analysis of the primary outcome variables of safety and tolerability will be carried out in the per-protocol population (PP), defined as any subject with an adherence $\geq 80\%$ determined by the subject's diary and corroborated by the final weight of the research product to which it was assigned (PRO-231 or VIGAMOXI)[®] with respect to its initial weight. and that they conclude their participation without deviations from the study protocol.

The Shapiro-Wilk test (S-W) will be used to determine if the distribution is normal in the data obtained in each study group ($p>0.05$). If the normality in the distribution of the data is verified, to rule out differences between groups, the Student's t-statistic will be used for independent groups, while intragroup differences will be analyzed with the Student's t-test for repeated measures.

In case of $p < 0.05$ in S-W, the statistical analysis to rule out differences between groups will be performed by means of the Mann-Whitney U test for quantitative variables, while intragroup differences will be performed by Wilcoxon's rank test.

For qualitative variables, Pearson's X² (Chi-square) or Fisher's exact test will be used in expected values less than 5. Dichotomous variables will be analyzed by the McNemar test when applicable.

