5.2 Criteria for elimination and/or substitution of subjects

5.2.1 Elimination Criteria

- Withdrawal of the consent form under information.
- Presentation of a serious adverse event, whether or not related to the PIs, that, in the judgment of the PI and/or the sponsor, could affect the patient's ability to continue with study procedures safely.
- Non-tolerability or hypersensitivity to any of the compounds used during the tests (fluorescein, tetracaine).
- No tolerability or hypersensitivity to any of the investigational drugs.
- Adherence < 80% determined by the subject's diary and corroborated by the final weight of the PI with respect to the initial weight.

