6.4 Procedure for monitoring and measuring adherence

For more than four decades, numerous investigations have been conducted on the appropriate way to measure and quantify medication adherence, however, none has reached a consensus to stand as the gold standard, both in cross-sectional and longitudinal studies. [23, 24, 25, 26, 27, 28, 29, 30]

There are different procedures to measure adherence to pharmacological interventions. The most common procedure includes self-reports, which include: interviews with the subject, questionnaires and self-monitoring diaries. Its strengths are speed, flexibility, low cost and ease of implementation; They have a high degree of specificity for non-adherence, however, the sensitivity and reliability for adherence is low. [30, 31]

The biochemical measurement of the drug, or its metabolite, is one of the methods that best confirms the use of the drug. However, in addition to raising costs and being impractical, it is of little use in the context of ophthalmic applications, since concentrations at the peripheral level could be undetectable; and samples of other tissues involve more invasive methods that would not be advisable. [30]

There is no standardized parameter to define adequate adherence, it must be defined and delineated by the objectives of the particular research. [30]

For this study, a minimum adherence of 80% (per subject's diary) will be considered to be necessary to meet the objectives of the research; In turn, the information in the diary will be corroborated with the final weight of the research product with respect to its initial weight. Therefore, subjects with adherence of less than 80% will not be considered for the study.

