7.4.2 Secondary outcome variables

7.4.2.1 Security

- Incidence of expected and intervention-related AEs (excluding conjunctival hyperemia and/or chemosis).

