F1	Presence of burning								B	TB				
F2	ETS Presence								B		TB			
F3	Presence of pruritus								B		TB			
F4	Presence of tearing								B		TB			

Abbreviations: AVMC, best corrected visual acuity; B, bivariate analysis; D, descriptive statistics; AE, adverse event; ICO, eye comfort index; SCE, foreign body sensation; T, contingency table p x q. *EAs related or not, with the research product.

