10.3.2.2 Analysis for secondary variables

The analysis of the secondary outcome variables of safety and tolerability will be carried out in the safety population, defined as any subject who has received at least one dose of the investigational product (PRO-231 or VIGAMOXI)[®] regardless of their adherence to it or adherence to the protocol (intention-to-treat population, ITT).

For the analysis of these variables, the same primary analysis will be carried out as long as they have the necessary measurements to do so.

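### The primary safety and tolerability variables are tested only in the per-protocol set, so subjects can leave the main comparison because of the outcome it measures

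*Combined protocol and SAP*

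**What the plan says.** Section 10.3.2.1 places every primary variable in one set: "The analysis of the primary outcome variables of safety and tolerability will be carried out in the per-protocol population (PP"). The variables are unexpected related adverse events, hyperemia and chemosis, best-corrected visual acuity, Oxford staining and the Eye Comfort Index (ICO). Members of the set must have adherence of at least 80%, by diary corroborated by bottle weight, "and that they conclude their participation without deviations from the study protocol". No distinction is made between major and minor deviations.

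Section 10.3.2.2 defines a second population, everyone with at least one dose "regardless of their adherence to it or adherence to the protocol (intention-to-treat population, ITT"), and assigns only the secondary variables to it. Section 10.4 adds no sensitivity analysis, and 10.4.1 provides no imputation.

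Section 5.2.1 eliminates subjects for "No tolerability or hypersensitivity to any of the investigational drugs" and for a serious adverse event judged to be one that "could affect the patient's ability to continue with study procedures safely". Section 6.4 says that "subjects with adherence of less than 80% will not be considered for the study".

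**The concern.** In a safety trial, the subjects who stop or under-dose may be those the product harms. Removing them takes events out of the numerator and subjects out of the denominator of the arm with more harm, so the observed difference shrinks.

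The decision rule makes this matter more. The table in 10.3.1 reads p ≥ 0.05 with a confidence interval (CI) that includes zero as the two products being similar, which is the result that 10.1.2 expects. The sentence under that table, and section 3.2, say that when the conditions are not met the result is only absence of evidence. These readings conflict. On the table's reading, outcome-dependent exclusion favours the expected conclusion.

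**Working it through.** **Routes out of the primary set**

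- Low adherence and deviations are excluded explicitly (10.3.2.1, 6.4).
- Elimination for intolerance, hypersensitivity or certain serious events (5.2.1) leads out by inference, because such subjects do not conclude participation.
- Section 8.4 defines a severe event as one that requires stopping the medication.
- Drug treatment of an event may be a prohibited medication (6.3.2), and so a deviation.
- Adherence: 3 drops × 7 days = 21 doses, and 80% of 21 is 16.8. Stopping after day 5 gives 15/21 = 71.4% (out); after day 6, 18/21 = 85.7% (in). Stopping at any time through day 5 fails the limit by itself.

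**What the secondary analysis recovers**

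- Ocular symptoms are covered.
- Section 7.4.2.1 defines the secondary event variable as "Incidence of expected and intervention-related AEs (excluding conjunctival hyperemia and/or chemosis"). This leaves out unexpected related events, hyperemia and chemosis.
- The footnote to Table 5 describes the corresponding row as "EAs related or not, with the research product". On that reading, unexpected events and threshold changes in acuity or staining, which count as adverse events under 7.4.4.4 and 7.4.4.5, would be included.
- On either reading the ICO, and acuity and staining changes below those thresholds, stay per-protocol only.

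**The plan's sample size**

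n per arm = [pA(1−pA) + pB(1−pB)] × ((z₀.₉₇₅ + z_power)/(pA − pB))², with pA = 0.50 for PRO-231 (10.1.1). Power is not stated.

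- pB = 6/62, 80% power: (0.250 + 0.0874) × (2.802/0.403)² = 16.3, so 17. This matches the plan but treats six events as six subjects.
- pB = 3/62: 11.4, so 12 at 80% power; 15.3, so 16 at 90%.
- The 10% allowance takes 17 to 19 per arm, that is, 2 subjects per arm.

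**Illustration by counts** (assumed counts; two-sided Fisher test; Newcombe 95% CI, since the plan names no method). The smallest expected count in 7/19 against 1/19 is 4.0, so the plan's own rule calls for Fisher.

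| Affected subjects removed | PRO-231 | Comparator | p | 95% CI | Equality rejected |
|---|---|---|---|---|---|
| 0 | 7/19 | 1/19 | 0.042 | 0.05 to 0.54 | yes |
| 1 | 6/18 | 1/19 | 0.042 | 0.02 to 0.51 | yes |
| 2 | 5/17 | 1/19 | 0.081 | −0.01 to 0.48 | no |
| 3 | 4/16 | 1/19 | 0.156 | −0.05 to 0.45 | no |

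Two subjects is the loss allowance for one arm. Three is 3/19 = 15.8%, below the 20% loss to follow-up that 5.5 calls unproblematic. Neither figure is an elimination rate; they serve only as yardsticks.

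**Chance of rejection over all tables** (exact binomial enumeration, 19 per arm; rejection needs p ≤ 0.05 and a CI excluding zero; a fraction q of subjects with an event is removed in both arms). The event rate left in the set is p(1−q)/(1−pq); from 50% it falls to 42.9% at q = 0.25 and 33.3% at q = 0.50.

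| Rates, test | q = 0 | 0.10 | 0.25 | 0.50 |
|---|---|---|---|---|
| 50% vs 6/62, Fisher | 72% | 71% | 65% | 47% |
| 50% vs 3/62, Fisher | 88% | 87% | 81% | 61% |
| 50% vs 6/62, plan's rule | 81% | 75% | 67% | 47% |
| 50% vs 3/62, plan's rule | 91% | 88% | 82% | 61% |

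The plan's rule is chi-square, or Fisher when an expected count is below 5.

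**The case against.** - **Coverage.** The operational definition of the secondary event row in Table 2 speaks of all intervention-related events, so that row may be wider than its title. This stands as an inconsistency, but the title still limits the row to expected events and excludes hyperemia and chemosis.
- **Other safeguards.** All events are recorded (8.3) and reported (8.5), subjects removed for events are followed (5.5), and serious events in more than 10% of a group can suspend the study (11.3). Signals would not be hidden. What is missing is a between-arm test of the primary variables in all dosed subjects.
- **The counts sit on an edge.** Against 1/19, seven is the smallest count that rejects (6/19 gives p = 0.090). With 8/19 and two removed (6/17, p = 0.037), 9/19 and three removed (6/16, p = 0.032), or 10/19 and four removed (6/15, p = 0.028), equality is still rejected. That is right. The example shows that two subjects can change the result, not that they usually will. The enumeration does not depend on that choice of table.
- **The 50% rate is a planning value.** At assumed rates of 20% against 5%, power with all dosed subjects is only about 15%; at 10% against 5%, about 1%. Sample size then dominates whichever set is used. That stands, but it is no reason to lose events as well.
- **Replacement.** Section 5.2.2 lets the sponsor replace subjects who withdraw consent or are lost to follow-up, so the smaller denominators may not occur. Replacement would not remove the selection.
- **Dilution.** Poor adherers in the at-least-one-dose set can also hide a difference, and per-protocol has a recognised role in a similarity claim. This supports reporting both sets, not per-protocol alone.

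**Conclusion.** The concern holds. The plan defines an at-least-one-dose population and does not use it for the variables that carry the main safety objective. Its own rules let intolerance, some serious events and under-dosing remove subjects from those tests. If one product causes more events and affected subjects leave, the bias runs towards no difference.

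Its size cannot be fixed from the documents. At the planning rates, the Fisher power loss is about one point if 10% of subjects with an event are excluded, about 6 to 7 points at 25%, and about 25 to 27 points at 50%. These figures assume the same exclusion fraction in both arms and no loss of subjects without an event. Exclusion after elimination under 5.2.1 is inferred; exclusion for low adherence or deviations is explicit. The remedy is cheap and affects every primary variable, so it should be settled before the data are seen.

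**What to change.** **Main change.** In 10.3.2.1, make the at-least-one-dose population of 10.3.2.2 the main set for all primary variables, keep per-protocol as supporting, and require both to be reported before similarity is concluded.

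**Details to specify**

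- State whether subjects are grouped by product assigned or received, since 10.3.2.2 calls the set both safety and intention-to-treat.
- Count adverse events, hyperemia and chemosis from all post-dose assessments, including unscheduled and withdrawal visits.
- Analyse acuity, staining and ICO in dosed subjects with observed post-baseline data, consistent with 10.4.1, and report missing subjects by arm and reason.

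**Clarifications, secondary to the main change**

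- In 5.5, say that the withdrawal visit counts as the final visit for everyone who stops early and includes the ICO. The present wording, with 7.7.3, may already mean this.
- In 6.4, say that low-adherence subjects stay in the safety analysis.
- Reconcile 7.4.2.1, Table 2 and the Table 5 footnote on the scope of the secondary event variable.
- Reconcile the table in 10.3.1 with the sentence beneath it.

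**Cost.** Protocol and SAP wording and a second set of tables. N stays 38 and the elimination criteria are unchanged. The downside is dilution by poorly adherent subjects, which the supporting per-protocol analysis is there to show.

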5.1 Eligibility Criteria

5.1.1 Inclusion criteria

- Have the ability to voluntarily give their signed informed consent.
- Ophthalmologically and clinically healthy subjects.
- Be able and willing to comply with scheduled visits, treatment plan, and other study procedures.
- Age 18 to 45 years.
- Both sexes.
- Women of childbearing potential must ensure continued use (initiated \geq 30 days prior to signing the CRF) of the use of a hormonal contraceptive method or IUD during the study period.
- AVMC of 20/30 or better in both eyes.
- Corneal staining \leq grade I on the Oxford Scale.
- Have an intraocular pressure \geq 10 and \leq 21 mmHg.

5.1.2 Exclusion criteria:

- History of hypersensitivity to fluoroquinolones or any of the components of the PI.
- Be a user of topical ophthalmic medications of any pharmacological group.
- Be a user of medicines by any other means of administration.
- History of eye surgery in the last 6 months.
- Wearing contact lenses for less than two weeks prior to the start of the study, and during the study intervention period.
- For women: being pregnant, breastfeeding, or planning to become pregnant within the study period.
- Have participated in any investigational clinical study 30 days prior to inclusion in this study.
- Have previously participated in this same study.
- History of any chronic-degenerative disease, including Diabetes Mellitus or Systemic Arterial Hypertension.
- Known diagnosis of liver or heart disease.
- Have active inflammatory or infectious disease at the time of study entry.
- Have unresolved injuries or trauma at the time of study entry.
- Having undergone surgical, non-ophthalmologic procedures within the past 3 months.
- Have received doses of vaccine against the Influenza virus or Coronavirus, 7 days prior to the inclusion of this study, or plan to receive it during the intervention of the same.

- Be or have an immediate family member (e.g., spouse, parent/legal guardian, sibling, or child) who is employed by the research site or sponsor, and who is directly involved in this study.
- Positive smoking (specified as cigarette smoking regardless of quantity and frequency, 4 weeks prior to study inclusion and during the study intervention period).
- Positive alcoholism (specified as the consumption of alcoholic beverages, regardless of quantity and frequency, 72 hours prior to the inclusion of the study and during the study intervention period).

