5.5 Procedure in case of loss of follow-up

For this protocol, loss of follow-up is defined as those subjects who were assigned the PI, who at some point were active subjects of the study, but their final evaluation could not be completed.

In the event that the subject does not terminate their participation due to withdrawal of consent or major deviation, the last visit, in which their withdrawal was determined, will be considered their final visit. Subjects who are removed due to the presence of AEs will continue with the follow-up that is defined until the closure of their AE.

In cases where the participating subject does not attend their appointment, the research center must make a call to find out the reason and will try to make a new appointment within the established window period or an unscheduled appointment. In the event that it is not possible to make an appointment, the subject will be considered as loss of follow-up and will be asked about the presence of adverse events and the reason for leaving the study, as minimum data.

A loss of follow-up <20% is considered not to be a problem for the validity of the results obtained.
[20, 21]

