6.1.3 Treatment with the investigational product

The product under investigation will be delivered at the conclusion of the baseline visit. The subject under investigation will begin the application the next day (day 1) by administering one drop every 6 hours, applying a total of one drop three times a day to the right eye during the 7 days of application.

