6.3.1 Permitted Medications

- Ophthalmic:

All permitted medications applied via ophthalmic medication during the study must wait a minimum period of 10 minutes from the last application of the treatments under study or reference. The above in order to avoid the interaction of treatments in the tear film, based on the flow index and physiological tear volume. [22]

- Tetracaína 0.5%
- Tropicamida 0.8% /Phenylephrine 5%
- Hipromelosa 2%
- Fluorescein

- Systemic:

In case participants of childbearing potential decide to use a hormonal contraceptive method, the following will be allowed:

- o Oral contraceptives.
- o Subdermal implant.
- o Parenteral injection.
- o HORMONAL DIU.

6.3.2 Prohibited medicines:

- Any ophthalmic or systemic medications that are not on the list of allowed medications.

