10.1.2 Size Calculation

PRO-231 ophthalmic solution is expected to be safe in its ophthalmic application as it presents an incidence of AE similar to that presented by VIGAMOXI.®

On this basis, a sample of 17 ophthalmologically and clinically healthy subjects was estimated. This value increased by 10% considering possible losses. Based on this consideration, 19 subjects per arm (38 subjects in total) are required to provide one eye (OD) to respond to the primary objective of the study.

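### The per-protocol set for all primary tests excludes subjects for any deviation, undefined and ungraded, and the allowance of two per arm is not sized for this

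*Combined protocol and SAP*

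**What the plan says.** Section 10.3.2.1 assigns all primary variables to the per-protocol set. Membership has two conditions: adherence of at least 80%, and completion such "that they conclude their participation without deviations from the study protocol". Section 10.3.2.2 puts the secondary variables in the all-treated population, regardless of adherence to product or protocol.

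Other sections bear on who would be excluded:

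- Section 6.4 sets the dosing threshold: "a minimum adherence of 80% (per subject's diary) will be considered to be necessary to meet the objectives of the research". Section 6.1.3 gives the schedule, "applying a total of one drop three times a day to the right eye during the 7 days of application".
- Section 5.1.2 rules out "the consumption of alcoholic beverages, regardless of quantity and frequency" from 72 hours before inclusion and through the intervention period, and has a similar rule for cigarettes.
- Section 6.3.2 prohibits "Any ophthalmic or systemic medications that are not on the list of allowed medications". The list in 6.3.1 holds diagnostic eye products and hormonal contraceptives only.
- The timeline in 7.6.2 gives the Day 3 visit and the Day 12 call a window of one day either side. The Day 8 final visit has none.
- Section 5.5 refers to a subject who "does not terminate their participation due to withdrawal of consent or major deviation". The idea of a graded deviation is therefore present, but it is not defined there or linked to the per-protocol set.

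On numbers, section 10.1.2 starts from 17 and states: "This value increased by 10% considering possible losses". This gives 19 per arm. Section 5.2.2 lets the sponsor replace subjects who withdraw consent or are lost to follow-up. It does not mention deviations or low adherence.

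**The concern.** Taken at its word, the second condition removes a subject from all primary tests for an unlisted tablet, a single drink or a final visit one day off, none of which need affect the study eye. Two analysts working from the same data could also build different primary sets, because the text does not say what a deviation is or whether a drop missed within the 80% allowance is one.

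Some exclusions may depend on the outcome. Section 8.4 defines moderate and severe adverse events partly by their needing treatment. If that treatment is a medicine outside the 6.3.1 list, the subject has, on a literal reading, deviated and leaves the primary adverse-event comparison.

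Smaller sets also mean less power. Section 10.3.1 reads a non-significant result whose interval includes zero as similarity, so on average lost power makes that conclusion easier to reach.

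**Working it through.** **1. The plan's own figure.** Inputs from 10.1.1: two-sided comparison of two proportions, 1:1 allocation, PRO-231 rate 0.50. Alpha is 0.05 (10.3.1). For the comparator, 10.1.1 reports 6 ocular adverse events and 3 patients with at least one event, among 62 treated with moxifloxacin. Power is not stated. I use both variance terms, as in the plan's power formula:

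n = [pA(1−pA) + pB(1−pB)] × [(1.960 + 0.842)/(pA−pB)]²

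- 6/62 at 80% power: (0.0874 + 0.25) × 7.849/0.4032² = 16.29, so 17.
- 3/62: 11.39, so 12 at 80% power; 15.25, so 16 at 90%.

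The first line matches the plan, but the input is inferred: the 3.2% conjunctivitis rate in 10.1.1 at 95% power gives 16.7, also rounding up to 17. Both 6/62 and 3/62 are therefore carried forward.

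Allowance: 17/0.90 = 18.9 and 17 × 1.10 = 18.7; both round up to 19. Room for exclusions is 19 − 17 = 2 per arm (2/19 = 10.5%).

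**2. Chance of keeping 17 per arm.** The documents give no exclusion rate d, so a range is assumed, with independent exclusions at the same rate in both arms. For one arm, P = P(X ≥ 17), X ~ Binomial(19, 1−d); for both arms, P².

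| Exclusion rate | Expected per arm | One arm ≥ 17 | Both arms ≥ 17 |
|---|---|---|---|
| 2% | 18.6 | 0.994 | 0.99 |
| 5% | 18.1 | 0.933 | 0.87 |
| 10% | 17.1 | 0.705 | 0.50 |
| 15% | 16.1 | 0.441 | 0.20 |
| 20% | 15.2 | 0.237 | 0.06 |
| 30% | 13.3 | 0.046 | 0.002 |

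**3. Missed drops, under each reading.** There are 3 × 7 = 21 drops; 80% of 21 is 16.8, so at least 17 must be taken and up to 4 may be missed. Assume the same miss rate m for everyone and independent misses. The probability of no missed drop is (1−m)²¹.

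- m = 0.5%: 0.900, so 17.1 of 19 expected; both arms reach 17 with probability 0.50.
- m = 1%: 0.810, so 15.4 expected; probability 0.07.
- m = 2%: 0.654, so 12.4 expected; probability about 0.

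Under the 80% rule alone, the same miss rates leave about 19 per arm. If misses cluster in a few subjects, more subjects take all 21 drops at the same average, so these are pessimistic figures for the stricter reading.

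**4. Power.** Plan's formula, with z = |pA−pB| / √{[pA(1−pA) + pB(1−pB)]/n}; power is Φ(z − 1.960), the other tail being negligible.

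- 6/62: n = 17, z = 2.862, power 0.82; n = 13, z = 2.503, power 0.71.
- 3/62: n = 17, z = 3.422, power 0.93; n = 13, z = 2.993, power 0.85.

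Thirteen per arm corresponds to about 30% exclusions.

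**The case against.** A reader might infer that the plan cannot deliver 17 per arm. The documents do not support that: they give no deviation rate, and at 5% exclusions both arms reach 17 with probability 0.87. Entry criteria select healthy non-smokers who use no other medicines, and treatment lasts 7 days, so the rate could be low. If the sponsor uses the optional replacement, ordinary dropout need not consume the two spare subjects per arm.

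A reader might also infer that the no-deviation condition cancels the 80% allowance. That follows only if a missed drop is a deviation, which no section says. Sections 5.2.1, 6.4 and 10.3.2.1 all treat 80% as the dosing threshold, and it is natural to let the specific rule govern dosing. The missed-drop figures apply only under the other reading.

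The power loss should not be quoted from 6/62 alone. Section 10.1.1 describes its input as the proportion of subjects with an event, which points to 3/62, and power then stays at 0.85 with 13 per arm. Nor does each exclusion push the result toward similarity: removing one subject can move a p-value either way. Treating non-significance as similarity is a separate issue that this change would not cure.

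These points limit the size of the concern. They do not supply a definition of a deviation or a limit on which ones exclude.

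**Conclusion.** The concern holds in a limited form. The no-deviation condition is a written rule for the set behind every primary test, and it has neither a definition nor a threshold. Taken literally, it drops subjects for reasons unrelated to the eye and possibly for reasons tied to the adverse events being compared. Whether it overrides the 80% dosing rule is ambiguous, not established.

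The 17 per arm is fairly safe at 5% total exclusions, an even chance at 10% and unlikely from about 15%. These probabilities rest on assumed rates, independence and equal risk in the two arms. Outcome-related exclusions would break the equal-risk assumption and could bias the comparison as well as shrink it. A fall to 13 per arm would cost 8 to 11 percentage points of power, depending on the comparator input. This is an inexpensive improvement worth making, not a flaw that invalidates the design.

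**What to change.** In section 10.3.2.1, restrict the second condition to major deviations and list them in advance as those that could affect a primary eye variable. Examples are wrong product, a failed eye-related eligibility criterion, a prohibited ophthalmic product in the study eye, or no final assessment. State that missed drops are judged only by the existing 80% criterion. Have masked staff fix the exclusion list before database lock; section 4.2 already masks the principal investigator and the person responsible for the statistical analysis. Keep all other subjects with deviations in the set and list their deviations in the report.

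The cost is a wording change in the protocol and SAP and one masked review meeting. No dose, visit or clinical rule changes. The downside is that some imperfect subjects stay in the set.
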